9.3 Other Safety Measures

9.3.1 Platelet Transfusions

[figure not shown]
A summary table will be created by prior TPO-RA (romiplostim and eltrombopag) and overall to display the frequency and percentage of enrolled subjects who have platelet transfusions (yes/no). The total number of platelet transfusions, and the reasons for transfusion (Thrombocytopenia, Bleeding Event, Adverse Event other than Bleeding Event, Other) will be summarized by category (subjects may appear in more than one category). The total number of packs/units received per transfusion will be summarized as a continuous variable.

Details of platelet transfusions occurring during the study will be presented in a listing.

9.3.2 World Health Organization Bleeding Scale

Bleeding will be assessed using the WHO Bleeding Scale according to verbal response. This assessment will be completed after the TSQM at the Baseline, Day 30, and Day 90 Visits. The Baseline WHO Bleeding Scale Assessment evaluates the severity of any bruising or bleeding the subject experienced within the 7 days prior to the Baseline Visit on Day 1. WHO Bleeding Scale assessed on Day 15, Day 30, Day 60, and Day 90 evaluates the severity of any bruising or bleeding the subject experienced since the previous visit.

The baseline assessment will be summarized in a table of baseline characteristics according to Section 6.1. A separate table will summarize WHO Bleeding Scale assessed on Day 15, Day 30, Day 60, and Day 90 which evaluates the highest severity of any bruising or bleeding the subject experienced since the previous visit (exclusive) including unscheduled visits up to the planned study visit. Bleeding for overall study period will also be presented which will include all schedule and unscheduled visits bleeding assessments and subjects are counted at the highest

Confidential

grade for the overall study period. A listing will be provided with details of the WHO Bleeding Scale assessment at all visits. The summary will be presented by prior TPO-RA (romiplostim and eltrombopag) and overall.

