7.4 Treatment Period (through Day 90)

7.4.1 Day 15 (± 2 Days)/Visit 3

- Perform WHO Bleeding Scale Assessment (Appendix B). The Investigator should ask the subject the following question: "Have you had any bleeding or bruising since I saw you last?". This assessment should be completed prior to other visit assessments.
- Collect and record platelet count (local lab).
- Record the occurrence of any platelet transfusion (including the number of units).
- Record whether the subject required any rescue procedure for bleeding.
- Review subject Dosing Diary and record any deviations from prescribed dosing regimen in the eCRF.
- Record any changes in avatrombopag dose and dose frequency.
- Dispense additional avatrombopag to the subject, as needed.
- Record any data on Additional Safety Information (Section 9.1.1) or AESIs (Section 9.5) that have occurred.
- Record any AEs.
- Record any concomitant medication use, including concomitant ITP medications.
- Instruct subject on when to return for the Day 30 Visit.

7.4.2 Day 30 (± 2 Days)/Visit 4

- Administer TSQM Version 1.4 to the subject.
- Perform WHO Bleeding Scale Assessment (Appendix B). The Investigator should ask the subject the following question: "Have you had any bleeding or bruising since I saw you last?". This assessment should be completed prior to other visit assessments.
- Collect and record platelet count (local lab).

- Record the occurrence of any platelet transfusion (including the number of units).
- Record whether the subject required any rescue procedure for bleeding.
- Review subject Dosing Diary and record any deviations from prescribed dosing regimen in the eCRF.
- Record any changes in avatrombopag dose and dose frequency.
- Dispense additional avatrombopag to the subject, as needed.
- Record any data on Additional Safety Information (Section 9.1.1) or AESIs (Section 9.5) that have occurred.
- Record any AEs.
- Record any concomitant medication use, including concomitant ITP medications.
- Instruct subject on when to return for the Day 60 visit.

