8.3 World Health Organization Bleeding Scale

Beginning with the Baseline Visit/Visit 2, the Investigator should assess bleeding using the WHO Bleeding Scale (Appendix B) according to verbal response.

During the Baseline Visit/Visit 2, the following question should be asked: "Have you experienced any bruising or bleeding within the last 7 days?".

At each subsequent visit, the following question should be asked: "Have you experienced any bruising or bleeding since I saw you last?".

This assessment should be completed *after* the TSQM at the Baseline, Day 30, and the Day 90 Visits.

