3.3 Study Design

This is a Phase 4, prospective, multi-center, open-label study to evaluate safety, platelet count, and subject reported medication satisfaction in adult subjects with chronic ITP after switching to avatrombopag from eltrombopag or romiplostim.

[figure not shown]
At least 100 subjects are planned to be enrolled, 50 (± 10) who have received eltrombopag and 50 (± 10) who have received romiplostim for at least 90 days prior to study entry. An overview of the study design is provided in [Figure 1](#).

The initial dose and dose adjustments of avatrombopag will be determined by the Investigator in conjunction with the DOPTELET® USPI (United States Prescribing Information). There is no protocol-required washout period between treatment with TPO-RAs (Thrombopoietin receptor agonists), however avatrombopag should not be administered on the same day as another TPO-RA. The start and stop dates of all prior and concomitant medications should be recorded in the electronic case report form (eCRF).

Safety will be evaluated throughout the study. Bleeding severity will be captured using the World Health Organization (WHO) Bleeding Scale at each visit. Platelet counts will be collected per protocol at Baseline, Day 15, Day 30, Day 60, and Day 90, however, all other platelet counts collected per the subject's standard of care while they are enrolled in the study should be recorded in the eCRF. The TSQM (Treatment Satisfaction Questionnaire for Medication) will be administered prior to the first dose of avatrombopag (at Baseline), at Day 30, and at Day 90 or at the time of early termination from the study. Compliance with the Investigator prescribed avatrombopag dosing regimen will be captured via a subject reported Dosing Diary which should be evaluated by the study team during each visit to the clinic, per the subject's standard of care.

Subjects may be screened within 28 days of the Baseline Visit/Visit 2; however, the Screening Visit/Visit 1 may be combined with the Baseline Visit/Visit 2. The duration of subject participation and collection of clinical data will be a minimum of 90 days from the Screening Visit/Visit 1 to Day 90. The only protocol-required clinic visits during the study are the Baseline Visit/Visit 2, Day 15, Day 30, Day 60, and the Day 90 or Early Termination Visit.

If a subject is early terminated, the early termination assessments should be completed prior to discharge from the study.

Figure 1: AVA-ITP-401 Study Schematic

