6.1 Demographics and Baseline Characteristics

Descriptive statistics with respect to subject characteristics at baseline will be displayed by prior TPO-RA (romiplostim and eltrombopag) and overall for all enrolled subjects. The variables to be summarized are:

Demographics

- Age at enrollment (years)
- Sex
- Race
- Ethnicity

Baseline subject characteristics

- TSQM domain scores of effectiveness, side effects, convenience, and global satisfaction
- Summary of WHO Bleeding Scale assessment (within the previous 7 days)
- Platelet count as assessed by local lab ($10^9/L$)

A listing of demographic and baseline characteristics will also be provided.

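### WHO bleeding is graded over 7 days at Baseline and over about 14, 15, 30 and 30 days at later visits, with no adjustment for length, so an unchanged bleeding rate can appear to rise

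*SAP*

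**What the plan says.** Protocol 8.3 sets two different questions. At Baseline the investigator asks "Have you experienced any bruising or bleeding within the last 7 days"; at every later visit the question is "Have you experienced any bruising or bleeding since I saw you last". Protocol 7.4 and Appendix A footnote e use the same two periods.

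SAP 9.3.2 carries this into the analysis. The Baseline grade refers to bleeding "the subject experienced within the 7 days prior to the Baseline Visit on Day 1", and each later grade "evaluates the severity of any bruising or bleeding the subject experienced since the previous visit". The required visits are "Baseline Visit/Visit 2, Day 15, Day 30, Day 60, and the Day 90 or Early Termination Visit" (SAP 3.3).

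The results go to two places. Baseline appears among the baseline characteristics, where SAP 6.1 lists it as "Summary of WHO Bleeding Scale assessment (within the previous 7 days)". For the four later visits, SAP 9.3.2 says: "A separate table will summarize WHO Bleeding Scale assessed on Day 15, Day 30, Day 60, and Day 90". They share this one table at the highest grade since the previous visit, with unscheduled grades counted towards the next planned visit. An overall-period highest grade is also shown. SAP 4.1.2 applies no visit windowing. The SAP plans no rate, common look-back, shift table, change from Baseline or test for the WHO grade.

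**The concern.** A worst grade over a period can only stay the same or go up as the period gets longer. The chance of any grade above 0 therefore depends on the length of the look-back as well as on the bleeding rate. Here the look-back is 7 days before the switch, about two weeks at the first two visits after it, and about a month at the last two.

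The study has one arm and no concurrent control, so bleeding over time is judged within subjects. A table in which the proportion with bleeding climbs between Day 30 and Day 60 invites the reading that control is being lost on avatrombopag, when the longer look-back alone could produce it. The opposite error is also possible: a real fall in bleeding could be cancelled by the longer look-back and read as no change.

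**Working it through.** **Inputs.**
- Visit days 1, 15, 30, 60 and 90, from Protocol Appendix A.
- Tolerance of ±2 days at each post-Baseline visit, from the same table.
- Baseline look-back of 7 days, from Protocol 8.3.
- The chance *p* of any bleeding in 7 days is an assumption. The documents give no bleeding rate, so a range of 2% to 30% is used. There is also no stated figure to reproduce.

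**Look-back lengths.** 15 − 1 = 14, 30 − 15 = 15, 60 − 30 = 30 and 90 − 60 = 30 days. With the tolerances the ranges are 12–16, 11–19, 26–34 and 26–34 days.

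**Model A: independent bleeds at a constant, unchanged rate.** P(any in *t* days) = 1 − (1 − *p*)^(*t*/7). For *p* = 0.10 and *t* = 30: 1 − 0.90^(30/7) = 36.3%.

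| Assumed 7-day chance | Day 15 (14 d) | Day 30 (15 d) | Days 60 and 90 (30 d) |
|---|---|---|---|
| 2% | 4.0% | 4.2% | 8.3% |
| 5% | 9.8% | 10.4% | 19.7% |
| 10% | 19.0% | 20.2% | 36.3% |
| 20% | 36.0% | 38.0% | 61.6% |
| 30% | 51.0% | 53.4% | 78.3% |

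**Model B: bleeding clusters in some subjects.** With gamma frailty of variance θ, P = 1 − (1 + θ*mt*)^(−1/θ), where *m* = [(1 − *p*)^(−θ) − 1]/(7θ) fixes the 7-day chance at *p*. For *p* = 0.10 and θ = 2, *m* = (0.90^(−2) − 1)/14 = 0.01675.

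**Model C: bleeds last a mean of *D* days.** With onset rate λ, the chance of already bleeding when the period opens is π = λ*D*/(1 + λ*D*), and P = π + (1 − π)(1 − e^(−λ*t*)). For *D* = 30 and *p* = 0.10, solving gives λ = 0.00295 and π = 0.081.

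Results with *p* = 0.10 and no true change:

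| Model | Baseline | Day 15 | Day 30 | Days 60 and 90 | Day 60 ÷ Day 30 |
|---|---|---|---|---|---|
| A, constant rate | 10% | 19.0% | 20.2% | 36.3% | 1.80 |
| B, variance 2 | 10% | 17.5% | 18.4% | 29.4% | 1.60 |
| B, variance 10 | 10% | 14.4% | 14.9% | 19.7% | 1.32 |
| C, 30-day bleeds | 10% | 11.8% | 12.1% | 15.9% | 1.31 |

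The direction is upward in every case; the size depends heavily on the assumptions.

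**Masking.** Under model A, the rate would have to fall to 7/14 = 50%, 7/15 = 47% and 7/30 = 23% of its Baseline value for Day 15, Day 30 and Days 60/90 to show the same percentage as Baseline.

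**Missed visit.** If Day 60 is missed, the Day 90 look-back becomes about 60 days. Model A with *p* = 0.10 then gives 1 − 0.90^(60/7) = 59.5%.

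**Check of equal intervals.** Day 1 to Day 30 is 29 days, followed by 30 and 30. With *p* = 0.10 and no true change, the three figures are 35.4, 36.3 and 36.3% under A; 28.8, 29.4 and 29.4% under B with variance 2; and 15.7, 15.9 and 15.9% under C. The artefact all but disappears under each model, whatever its size was.

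**The case against.** A reader might infer that Baseline and the later visits stand side by side in one by-visit table. They do not. SAP 9.3.2 puts Baseline in the baseline characteristics table, and SAP 6.1 labels its 7-day period. With no change from Baseline, shift table or test planned, the rise from Baseline arises only if a reader compares the two tables. That stands.

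The Baseline grade is also not the only information on bleeding before the switch. SAP 6.3 summarizes previous significant bleeding events, ITP hospitalizations and platelet transfusions. It is, however, the only WHO grade before the switch.

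The size is uncertain. The 36% figure is at the high end of the models run with a 10% starting value, and fading recall over a month would reduce it further. The actual look-back can also be shorter than the gap between protocol visits: the question is "Have you had any bleeding or bruising since I saw you last", standard-of-care visits may fall in between, and Protocol 7.4.4 records a WHO grade there only if it was collected as part of standard care. These points weaken the magnitude, not the direction shown by the models.

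Bleeding is further covered as treatment-emergent adverse events and as an event category of special interest (SAP 9.2). The overall-period highest grade does not depend on visit spacing, and the two prior-treatment columns share the same nominal look-back at each visit. All of this limits the consequence. It does not address the unequal columns inside the single post-Baseline table. The mock tables are in a separate document, so footnotes there could not be checked.

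**Conclusion.** The point holds as a weakness in a supporting safety display. The four post-Baseline columns cover about 14, 15, 30 and 30 days without adjustment, and the doubling between Day 30 and Day 60 lies inside one table, so that part needs no cross-comparison with Baseline. For an assumed 7-day chance of 10% and no true change, Day 60 would exceed Day 30 by a factor of about 1.3 to 1.8, and Days 60 and 90 would show roughly 16 to 36% against 10% at Baseline. These figures rest on an assumed rate and on new bleeds accruing over time.

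Two stronger readings are not supported. The documents do not show that bleeding will appear to rise, only that it can. Nor is the primary endpoint affected: it is the occurrence of adverse events and serious adverse events, which are not summarized by WHO look-back period.

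**What to change.** 1. **SAP 9.3.2.** Keep the by-visit columns, including Day 15, and label each with its look-back length. Add three intervals of about 30 days: Days 1–30 (the worst of the Day 15, Day 30 and intervening unscheduled grades), Days 31–60 and Days 61–90. Describe any trend from these intervals only. Do not count as a full interval a grade whose look-back spans a missed visit, or a partial period ended by early termination. State that the overall-period highest grade excludes Baseline; the current text does not settle this.

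2. **Protocol 8.3 and Appendix A footnote e, if data collection is still open.** At each post-Baseline visit keep the existing question and also grade the last 7 days. Use only that 7-day grade for comparison with Baseline. If collection has ended, state in the table that the 7-day Baseline grade is not comparable with the later visits.

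The first change is a SAP edit using grades already planned for collection, at the cost of a slightly longer table. The second costs one extra question and one eCRF field per visit.

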4.1 Study Period and Visit Window Definitions

4.1.1 Study Periods

Screening Period: Starting the day of the Screening Visit/Visit 1 in which informed consent is signed up to the day before the Baseline Visit/Visit 2 during which avatrombopag is first administered. The Screening Visit must be completed

Confidential

within 28 days prior to the Baseline Visit, however, the Screening and Baseline visits may be combined.

Treatment Period: Starting from the Baseline Visit/Visit 2 (or combined Visit 1/Visit 2, if applicable) through the End of Study Visit on Day 90 (± 2 days) or the Early Termination Visit, whichever occurs first.

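### Does the overall-period WHO bleeding summary in SAP 9.3.2 count bleeding from before the switch to avatrombopag?

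*SAP*

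**What the plan says.** SAP 9.3.2 plans three displays of the WHO bleeding grade, besides a listing.

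- **Baseline.** The assessment grades "bleeding the subject experienced within the 7 days prior to the Baseline Visit on Day 1". Its destination is stated: "The baseline assessment will be summarized in a table of baseline characteristics according to Section 6.1". SAP 6.1 lists the matching item: "Summary of WHO Bleeding Scale assessment (within the previous 7 days").
- **By visit.** A separate table covers Days 15, 30, 60 and 90. Each entry is the worst grade "since the previous visit (exclusive) including unscheduled visits up to the planned study visit".
- **Overall.** "Bleeding for overall study period will also be presented which will include all schedule and unscheduled visits bleeding assessments". Each subject is classified once, by the worst grade seen.

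Protocol 8.3 makes Baseline the first scheduled WHO assessment: "Beginning with the Baseline Visit/Visit 2, the Investigator should assess bleeding using the WHO Bleeding Scale". At every later visit the question is "Have you experienced any bruising or bleeding since I saw you last". SAP 4.3.3 treats assessments on the first dosing day as pre-dose unless specified otherwise. SAP 4.1.1 defines a Screening Period and a Treatment Period, the latter "Starting from the Baseline Visit/Visit 2 (or combined Visit 1/Visit 2, if applicable) through the End of Study Visit on Day 90" or early termination. It does not define an overall study period. Protocol 10.2.1 says only that bleeding reported in the course of the study is summarized by WHO grade.

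**The concern.** The overall sentence draws on all scheduled assessments, Baseline is one of them, and nothing in either document expressly takes it out. Because the summary uses a maximum, a single pre-dose grade can determine a subject's category.

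Take a subject with grade 2 in the week before the switch, a grade that Protocol Appendix B labels clinically significant, and grade 0 at every later visit. Word for word, that subject is grade 2 for the overall period although all four by-visit entries are 0. A subject with no assessment after dosing would receive an overall grade from Baseline alone.

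The study is about safety after leaving eltrombopag or romiplostim. A summary that mixes in bleeding on the previous drug would not describe that, and the error could only make bleeding look worse.

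**Working it through.** The plan gives no figure to reproduce here. The check is a comparison of texts, followed by the size of the effect per subject.

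**1. Is Baseline a scheduled, pre-dose assessment?** Yes. Both schedules of events mark the WHO scale at Baseline, and Protocol 7.3 places it before the first dose.

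**2. Does any sentence exclude it from the overall summary?** No. I looked at Protocol 7.3, 8.3, 10.2.1 and Appendix A, and at SAP 4.1.1, 4.3.3, 6.1, 9.3.2 and Appendix A.

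**3. What does the order of the SAP 9.3.2 paragraph imply?** Baseline is sent to the Section 6.1 table. A separate table is then opened for Days 15 to 90, with unscheduled visits folded in. The overall summary is added next, with the word *also*. The scheduled and unscheduled visits it refers to are most naturally those just described.

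**4. Do the two arguments for inclusion hold?**

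- *The Treatment Period begins at the Baseline Visit.* The date of the assessment is not the date of the bleeding. The Baseline question covers the 7 days before that visit, which lie outside the Treatment Period. With a combined Screening and Baseline Visit they precede the study altogether. With a separate Screening Visit, some of those days can fall in the Screening Period. The definition therefore settles nothing either way.
- *The by-visit sentence has a limit and the overall sentence has none.* The limit in "since the previous visit (exclusive) including unscheduled visits up to the planned study visit" stops neighbouring visit intervals from overlapping. A maximum over the whole period needs no such boundary, so its absence does not show an intention to include Baseline.

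**5. Size if Baseline were included.** Let B be the Baseline grade and M the highest grade after Baseline. The literal rule reports max(B, M), which is never below M and differs from it only when B > M.

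| Reading | Grades used in the example | Overall grade |
|---|---|---|
| Post-baseline only | 0, 0, 0, 0 | 0 |
| Literal | 2, 0, 0, 0, 0 | 2 |

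If k subjects in a column of n cross a given grade only because of Baseline, the percentage at or above that grade rises by k/n. Column sizes come from the planned 50 (±10) per prior drug and at least 100 in total:

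- n = 60: 1/60 = 1.7 points per subject
- n = 50: 1/50 = 2.0 points
- n = 40: 1/40 = 2.5 points
- overall, n = 100: 1/100 = 1.0 point
- overall, n = 120 (two columns of 60): 1/120 = 0.8 point

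The documents give no bleeding rates for this setting, so k cannot be estimated. It may be zero.

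**6. What depends on the result?** Protocol 3.1 and 3.2 name adverse events, TSQM domain scores and platelet response as endpoints. WHO grade is not among them. No test or stopping decision uses the overall summary. Bleeding adverse events of special interest are summarized as treatment-emergent under SAP 9.2, where the first-dose limit is explicit.

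**The case for a change.** The best case for a change is that a rule for selecting records belongs in the SAP and should not rest on context. Two competent programmers could produce different numbers from this sentence. The SAP does write limits where it wants them, as in the treatment-emergent definition in 9.2. Sending Baseline to one table does not by itself bar it from another. This is also the only planned subject-level summary of WHO grade across the whole period, the bias has one direction, and the repair would take a few words.

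Most of that is true as far as it goes. The qualifier is unwritten, and adding *post-baseline* would be harmless. What does not stand is the stronger claim that the plan is wrong. The literal reading pulls one sentence out of a paragraph that has already dealt with Baseline, and the two supporting arguments fail to show that Baseline was meant to be counted. SAP 4.4 and Section 11 leave display details to separate mock tables, which are not available here and may already settle the point.

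Nor would restricting to post-baseline be perfectly lossless. Under SAP 4.3.3, an unscheduled Day 1 assessment made after dosing would be treated as pre-dose unless marked otherwise, and the next visit asks only about bleeding since the subject was last seen. Such a case would be rare, and an assessment known to follow the dose should be kept.

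**Conclusion.** No change is needed. SAP 9.3.2 leaves unsaid whether the overall WHO summary includes Baseline, but the paragraph points to post-baseline assessments, and analysts would probably apply that reading without being told. This is missing detail in one descriptive safety summary.

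If the literal rule were programmed, the shift would be 1.7 to 2.5 percentage points per affected subject in a prior-treatment column and 0.8 to 1.0 point overall, always upward, for an unknown and possibly zero number of subjects. No endpoint, test or decision would move. The planned listing of the assessment at all visits would allow the post-baseline maximum to be rebuilt subject by subject, and the Baseline and by-visit tables would help a reader see the discrepancy.

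The conclusion rests on two assumptions: that the mock tables do not direct the literal reading, and that column sizes stay within the planned range.
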